4 STUDY DESIGN

4.1 Overall design

PS0032 is a Phase 3, multicenter, randomized, double-blind, placebo-controlled, parallel group study to evaluate the efficacy and safety of bimekizumab compared with placebo in adult Korean study participants with moderate to severe plaque PSO.

The study population consists of adult Korean study participants (≥ 19 years of age) with a diagnosis of moderate to severe plaque PSO (Baseline PASI ≥ 12 and BSA affected by PSO $\geq 10\%$ and IGA score ≥ 3 on a 5-point scale) who are candidates for systemic PSO therapy and/or phototherapy.

This study will include 3 periods: Screening Period (2 to 5 weeks), Treatment Period (16 weeks), and SFU Period (20 weeks after the last dose of IMP [Figure 1-1]).

Study participants who have completed the 16-week Treatment Period may choose to enter into a MAP to receive open-label treatment with bimekizumab or enter the SFU.

The Screening Period will last 2 weeks, but can be extended up to a total of 5 weeks in cases where a laboratory assessment needs to be repeated or to allow washout of prohibited medications. During the Screening Period, eligible study participants will be informed about the study and sign the ICF. Following signed informed consent, all screening procedures and laboratory tests (hematology, urine, and biochemistry) will be performed per the SoA (Table 1-1). The Screening Period will also enable washout of any medications not permitted for use during the study. Study participants who require prophylaxis for LTB infection must be on treatment for at least 4 weeks prior to the first dose of IMP. These study participants may be rescreened after receiving prophylaxis treatment. One rescreening may be allowed after consultation with the Medical Monitor. Further details are provided in Section 5.4.

After completion of the Screening Period, eligible study participants will be allowed to enroll into the study. Approximately 45 adult Korean study participants will be randomized 2:1 to receive the following blinded IMP regimens during the Treatment Period:

- Bimekizumab 320mg Q4W administered sc injection (30 study participants)
- Placebo Q4W administered sc injection (15 study participants)

During the Treatment Period, IMP will be administered at the study site.

All study participants choosing not to transition into a MAP (see Section 6.8) will have a SFU Visit 20 weeks post last dose of IMP. Safety assessments will be made by ongoing monitoring and evaluation of AEs and other safety topics of interest specific to bimekizumab.

Study participants withdrawing early from IMP will undergo the PEOT Visit assessments and be asked to continue in the SFU Period.

IMP administration and all assessments to be performed during the study are presented in the SoA (Table 1-1).

4.2 Scientific rationale for study design

This bimekizumab Phase 3 local clinical study in Korean study participants with PSO is designed to support a bridging data submission package for approval of the PSO indication in Korea. Previously it was demonstrated in a dedicated Phase 1 PK study (UP0042) that the PK/PD profile of Caucasian and Asian study participants is largely comparable. In addition, subgroup analyses of the Phase 2 (PS0010 and PS0011) and Phase 3 (PS0009) PSO studies have indicated that results of the Asian population were comparable to those of the overall population. Population PK/PD analyses revealed a clear dose-response relationship and support the use of bimekizumab at an initial dose regimen of 320mg Q4W to ensure rapid and high skin clearance, followed by a less intense dose regimen (320mg Q8W) in the majority of study participants to maintain these initial responses beyond Week 16.

The clinical response obtained in the global PSO development program (PS0008, PS0009, and PS0013) at Week 16 was consistently maintained through one year in study participants receiving either bimekizumab 320mg Q4W or bimekizumab 320mg Q8W, supporting the rationale for a 16-week study. This study aims to demonstrate the superiority of clinical response to bimekizumab over placebo in Korean study participants to those of the overall population during the initial Treatment Period of 16 weeks, allowing for adequate extrapolation of results in the maintenance period.

4.3 Justification for dose

Bimekizumab 320mg Q4W treatment effects in the initial 16-week treatment period were rapid (PASI75 achieved after a single dose) and deep (complete PSO clearance demonstrated by PASI100 and IGA 0). Approximately 85% to 90% of study participants achieved a high level of response (PASI90) after 16 weeks of bimekizumab 320mg Q4W treatment.

Study PS0032 has been designed to mimic the initial Treatment Period of the 3 global Phase 3 studies (PS0008, PS0009, and PS0013) and evaluate the efficacy and safety of bimekizumab 320mg, administered sc Q4W, in Korean study participants to allow bridging to the global Phase 3 data.

4.4 End of study definition

A study participant is considered to have completed the study if he/she has completed the Treatment Period of the study (Week 16) regardless of transfer into the MAP or completion of the SFU visit (see Section 6.8).

The end of the study is defined as the date of the LPLV in the study.

5 STUDY POPULATION

Prospective approval of protocol deviations to recruitment and enrollment criteria, also known as protocol waivers or exemptions, is not permitted.

5.1 Inclusion criteria

Study participants are eligible to be included in the study only if all of the following criteria are met at Screening and reconfirmed at the Baseline Visit:

Age

1. Study participant must be at least 19 years of age at the time of signing the informed consent.

Type of participant and disease characteristics

2. Study participant must be a Korean adult with a diagnosis of moderate to severe PSO.
3. Study participant must have had plaque PSO for at least 6 months prior to the Screening Visit.
4. Study participant must have PASI ≥ 12 and BSA affected by PSO $\geq 10\%$ and IGA score ≥ 3 on a 5-point scale.
5. Study participant must be a candidate for systemic PSO therapy and/or phototherapy.
6. Study participant agrees not to change their usual sun exposure during the course of the study and to use ultraviolet A/ultraviolet B sunscreens if unavoidable exposure occurs.
7. Study participant is considered reliable and capable of adhering to the protocol (eg, able to understand and complete diaries), visit schedule, or medication intake according to the judgment of the Investigator.

Sex

8. A female study participant is eligible to participate if she is not pregnant (see Section 10.4 [Appendix 4]), not breastfeeding, and at least one of the following conditions applies:
 - Not a female of childbearing potential (FOCBP) as defined in Section 10.4 (Appendix 4)
OR
A FOCBP who agrees to follow the contraceptive guidance in Appendix 4 during the Treatment Period and for at least 20 weeks after the last dose of study treatment.

Informed consent

9. Study participant must be capable of giving signed informed consent as described in Section 10.1 (Appendix 1), which includes compliance with the requirements and restrictions listed in the ICF and in this protocol.

5.2 Exclusion criteria

Study participants are excluded from the study if any of the following criteria apply:

Medical conditions

1. Study participant has a form of PSO other than plaque-type (eg, pustular, erythrodermic and guttate PSO, or drug-induced PSO).
2. Study participant has an active infection or history of infections as follows:
 - Any active infection (except common cold) within 14 days prior to Baseline.
 - A serious infection, defined as requiring hospitalization or intravenous anti-infectives within 2 months prior to the Baseline Visit.
 - A history of opportunistic, recurrent, or infections that, in the opinion of the Investigator, might cause this study to be detrimental to the study participants. Opportunistic infections are infections caused by uncommon pathogens (eg, pneumocystis jirovecii, cryptococcosis) or unusually severe infections caused by common pathogens (eg, cytomegalovirus, herpes zoster).
3. Study participant has concurrent acute or chronic viral hepatitis B or C or human immunodeficiency virus (HIV) infection, or history of hepatitis B. Study participants who have evidence of, or tested positive for hepatitis B are excluded. A positive test for the hepatitis B virus (HBV) is defined as:
 - positive for hepatitis B surface antigen (HBsAg+) **or**
 - positive for anti-hepatitis B core antibody (HBcAb+).A positive test for the hepatitis C virus (HCV) is defined as:
 - positive for hepatitis C antibody (anti-HCV Ab) **and**
 - positive via a confirmatory test for HCV (eg, HCV polymerase chain reaction).
4. Study participant has a known tuberculosis (TB) infection, is at high risk of acquiring a TB infection, or has a current or history of nontuberculous mycobacterium (NTMB) infection. A study participant with LTB (a positive interferon-gamma release assay [IGRA] and diagnosis confirmed by a TB specialist) may be rescreened once and enrolled after receiving at least 4 weeks of appropriate LTB infection therapy and if no evidence of therapy-related hepatotoxicity has occurred prior to the first injection (alanine aminotransferase/aspartate aminotransferase [ALT/AST] remain $\leq 3 \times$ upper limit of normal [ULN]).
Study participant has a past history of active TB involving any organ system unless adequately treated according to World Health Organization (WHO)/Centers for Disease Control (CDC) therapeutic guidance and proven to be fully recovered upon consult with a TB specialist.
5. Study participant has a history of a lymphoproliferative disorder, including lymphoma, or current signs and symptoms suggestive of lymphoproliferative disease.

6. Study participant has any active malignancy or history of malignancy within 5 years prior to the Screening Visit EXCEPT treated and considered cured cutaneous squamous or basal cell carcinoma, or in situ cervical cancer.
7. Study participant has a diagnosis of inflammatory conditions other than PSO or PsA, including but not limited to rheumatoid arthritis, sarcoidosis, or systemic lupus erythematosus. Study participants with a diagnosis of Crohn's disease or ulcerative colitis are allowed as long as they have no active symptomatic disease at Screening or Baseline.
8. Study participant has any systemic disease (ie, CV, neurological, renal, liver, metabolic, gastrointestinal, hematological, immunological, etc.) considered by the Investigator to be uncontrolled, unstable, or likely to progress to a clinically significant degree during the course of the study.
9. Study participant has had myocardial infarction or stroke within the 6 months prior to the Screening Visit.
10. Study participant has experienced primary failure (no response within 12 weeks) to 1 or more IL-17 biologic response modifier (eg, brodalumab, ixekizumab, secukinumab) **OR** more than 1 biologic response modifier other than an IL-17.
11. Study participant has a history of alcohol or drug abuse within 6 months prior to Screening as evaluated by the Investigator based on medical history, site interview, and/or results of the specified urine drug screen.
12. Study participant has a presence of active suicidal ideation, or positive suicidal behavior using the Columbia Suicide Severity Rating Scale (C-SSRS) and with either of the following criteria:
 - History of a suicide attempt within the 5 years prior to the Screening Visit. Study participants with a history of a suicide attempt more than 5 years ago should be evaluated by a mental healthcare practitioner (HCP) before enrolling into the study.
 - Suicidal ideation in the past month as indicated by a positive response ("Yes") to either Question 4 or Question 5 of the C-SSRS.
13. Study participant has a presence of moderately severe major depression or severe major depression indicated by a score ≥ 15 using the Screening PHQ-9. Medication used to treat depression should be stable for 8 weeks prior to Baseline.
14. Study participant has a known hypersensitivity to any excipients of bimekizumab.
15. Study participant has any other condition, including medical or psychiatric, which, in the Investigator's judgment, would make the study participant unsuitable for inclusion in the study.

Prior/concomitant therapy

16. Study participant has received any live (includes attenuated) vaccination within the 8 weeks prior to the Baseline visit (eg, inactivated influenza and pneumococcal vaccines are allowed but nasal influenza vaccination is not permitted). Live vaccines are not allowed during the study, including the SFU Period (20 weeks after the final dose of IMP).

Administration of any other type of vaccine that is not a live or inactivated vaccine must be discussed with the study Medical Monitor or UCB Study Physician.

17. Study participant has received Bacillus Calmette-Guerin vaccinations within 1 year prior to the Baseline visit.
18. Study participant has had major surgery (including joint surgery) within the 3 months prior to the Baseline Visit or has planned major surgery within the duration of the study.
19. Study participant is taking or has taken prohibited PSO medications (Section 6.5.2) without meeting the mandatory washout period relative to the Baseline Visit.

Prior/concurrent clinical study experience

20. Study participant previously participated in a bimekizumab clinical study and received at least 1 dose of the IMP (including placebo).
21. Study participant previously participated in another study of a medication (systemic) under investigation within the 12 weeks or at least 5 half-lives prior to the Screening Visit, whichever is greater, or is currently participating in another study of a medication (systemic) under investigation.
22. Study participant previously participated in another study of a topical medication under investigation within the 4 weeks prior to the Screening Visit, or is currently participating in another study of a topical medication under investigation.
23. Study participant previously participated in another study of a medical device under investigation within the 4 weeks prior to the Screening Visit, or is currently participating in another study of a medical device under investigation.

Diagnostic assessments

24. Study participant has laboratory abnormalities at Screening, including any of the following:
 - $\geq 3 \times \text{ULN}$ of any of the following: ALT, AST, alkaline phosphatase (ALP); or $> \text{ULN}$ total bilirubin ($\geq 1.5 \times \text{ULN}$ total bilirubin if known Gilbert's syndrome)
 - White blood cell (WBC) count $< 3.00 \times 10^3 / \mu\text{L}$
 - Absolute neutrophil count $< 1.5 \times 10^3 / \mu\text{L}$
 - Lymphocyte count $< 500 \text{ cells} / \mu\text{L}$
 - Hemoglobin $< 8.5 \text{ g} / \text{dL}$

Any other laboratory abnormality, which, in the opinion of the Investigator, will prevent the study participant from completing the study or will interfere with the interpretation of the study results.

Individual screening tests for which the results are in error, borderline, or indeterminate for inclusion in the study can be repeated once for confirmation during the Screening Period. Upon retesting, study participants whose results remain outside this threshold should not be randomized.

Other exclusions

25. Study participant is a member of Investigator site personnel directly affiliated with this study and/or their immediate families. Immediate family is defined as a spouse, parent, child, or sibling, whether biological or legally adopted.
26. Study participant is a UCB employee or an employee of third-party organizations involved in the study.

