The study participant must be permanently withdrawn if further examinations result in a diagnosis of active TB, or if the study participant is diagnosed with LTBI with no initiation of prophylactic treatment, prematurely discontinues prophylactic treatment, or, in the opinion of the Investigator or Sponsor, is noncompliant with prophylactic TB therapy.

Confirmed active TB is an SAE and must be captured on an SAE Report Form and provided to the Sponsor in accordance with SAE reporting requirements. As with all SAEs, periodic follow-up reports should be completed as per protocol requirements until such time as the TB infection resolves.

Additional information on TB policies is provided in Section 8.2.7.

9. Study participants with newly diagnosed IBD or IBD flares during the study must:
 - Be referred, as appropriate to a health care professional treating IBD, such as a gastroenterologist
 - Discontinue IMP and be followed-up until resolution of active IBD symptoms
 - If IBD flares increase in severity or frequency during the study, the Investigator should use clinical judgement in deciding whether the study participant should continue in the

study and contact the Medical Monitor and UCB Study Physician to confirm the study participant's suitability for continued participation in the study.

10. Study participants **must be referred** immediately to a mental health care professional and may be withdrawn from the study based upon the Investigator's judgment of benefit/risk for:

- Active suicidal ideation as indicated by a positive response (“Yes”) to Question 4 of the “Since Last Visit” version of the C-SSRS.
- Moderately severe major depression as indicated by a PHQ-9 score of 15 to 19 if this represents an increase of 3 points compared to last visit.

11. Study participants **must be referred** immediately to a mental health care professional and must be withdrawn from the study in case of:

- Active suicidal ideation as indicated by a positive response (“Yes”) to Question 5 of the “Since Last Visit” version of the C-SSRS.
- Any suicidal behavior since last visit.
- Severe major depression as indicated by a PHQ-9 score ≥ 20 .

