Study participants must be referred immediately to a mental health care professional for further assessment of any suicidal ideation/behavior (SIB) and/or any evidence of major depression. Investigators should contact the Medical Monitor, whenever possible, to discuss the withdrawal of a study participant in advance. Withdrawal is mandatory for suicidal behavior and/or a confirmed diagnosis of severe major depression. Otherwise, a withdrawal decision will be based on the Investigator's assessment of benefit/risk. The mental health consultation will be documented in source documentation.

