8.2.6 Neuropsychiatric AE monitoring/suicidal risk monitoring

Suicidal ideation and behavior will be assessed by using the C-SSRS. The questionnaire will be administered and assessed by trained study personnel. This scale will be used to assess suicidal ideation and behavior that may occur during the study. The visits at which the C-SSRS assessments will be performed are specified in the SoA (Table 1-1).

The C-SSRS is a standardized and validated instrument developed for the assessment of the severity and frequency of suicidal ideation and behavior (Posner et al, 2011; Mundt et al, 2010). Participants respond to standardized clinical questions that are presented in a uniform fashion. The C-SSRS defines 5 subtypes of suicidal ideation and behavior in addition to self-injurious behavior with no suicidal intent. The C-SSRS takes approximately 3 to 10 minutes to complete.

Refer to Section 7.1 for C-SSRS-related IMP discontinuation.

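### As printed, exclusion criterion 12 does not by itself exclude recent suicidal behavior short of an attempt, although any new suicidal behavior on study requires withdrawal

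*Protocol*

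**What the plan says.** **At entry (Protocol Section 5.2).** The stem of criterion 12 covers a participant with "presence of active suicidal ideation, or positive suicidal behavior using the Columbia Suicide Severity Rating Scale (C-SSRS) and with either of the following criteria". Two bullets follow. The first is "History of a suicide attempt within the 5 years prior to the Screening Visit"; older attempts call for an evaluation by a mental health practitioner before enrollment. The second is a 'Yes' to C-SSRS Question 4 or 5 in the past month. Criterion 13 reads "Study participant has a presence of moderately severe major depression or severe major depression indicated by a score" of at least 15, on the PHQ-9 done at Screening. Criterion 15 lets the Investigator exclude for "any other condition, including medical or psychiatric", as a matter of judgment.

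**On study (Protocol Section 7.1).** Item 10 requires mental health referral, and leaves withdrawal to the Investigator, for a 'Yes' to Question 4 or for "Moderately severe major depression as indicated by a PHQ-9 score of 15 to 19 if this represents an increase of 3 points" since the last visit. Item 11 requires referral and withdrawal for a 'Yes' to Question 5, for "Any suicidal behavior since last visit", or for a PHQ-9 score of 20 or more. The closing paragraph repeats the rule: "Withdrawal is mandatory for suicidal behavior and/or a confirmed diagnosis of severe major depression".

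**Measurement.** The schedule of activities (Table 1-1) places the C-SSRS at both Screening and Baseline. Section 8.2.6 adds: "The questionnaire will be administered and assessed by trained study personnel".

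**The concern.** The word 'and' at the end of the stem makes positive suicidal behavior exclusionary only when one of the bullets is also met. One bullet concerns attempts and the other concerns ideation. Neither describes suicidal behavior that stops short of an attempt. A participant with such behavior shortly before Screening, and 'No' to Questions 4 and 5, does not meet criterion 12 as written.

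Suicidal ideation and behavior is a prespecified safety topic (Protocol Section 2.3). Once a participant is on study, the protocol takes the withdrawal decision for suicidal behavior away from the Investigator. For recent non-attempt behavior at entry, it leaves the decision with the Investigator. A site that reads the 'and' as 'or' would exclude this participant and a literal site would not, so eligibility could differ by site. Waivers of entry criteria are not allowed (Section 5), and exclusion-criteria deviations are a category of important protocol deviation (Section 9.5), so the printed wording carries weight.

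**Working it through.** The plan gives no figure on this point, so the check sets the rules side by side.

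**Step 1: the logic of criterion 12.** Let A = active suicidal ideation, B = positive suicidal behavior on the C-SSRS, C = attempt within 5 years, D = 'Yes' to Question 4 or 5 in the past month. Take two profiles:

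- Profile 1, non-attempt behavior only: A = 0, B = 1, C = 0, D = 0.
- Profile 2, active ideation only, without a 'Yes' to Question 4 or 5: A = 1, B = 0, C = 0, D = 0.

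| Reading | Rule | Profile 1 | Profile 2 |
|---|---|---|---|
| 1. Stem joined to bullets | (A or B) and (C or D) | (0 or 1) and (0 or 0): not excluded | (1 or 0) and (0 or 0): not excluded |
| 2. Comma separates ideation | A or [B and (C or D)] | 0 or [1 and 0]: not excluded | 1 or [0 and 0]: excluded |
| 3. Bullets only | C or D | 0 or 0: not excluded | 0 or 0: not excluded |
| 4. 'And' replaced by 'or' | A or B or C or D | excluded | excluded |

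Profile 1 is excluded only under reading 4, which changes a printed word. Profile 2 matters for the remedy: it is excluded under readings 2 and 4, so a rewording that dropped active ideation would loosen the criterion under those readings. Whether profile 2 can occur depends on what counts as active ideation. Section 7.1 uses that term for a 'Yes' to Question 4 or 5, but the protocol does not say that it is limited to those answers. The result for profile 1 is the same either way.

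**Step 2: entry rule against on-study rule.** Items 10 and 11 hold 2 + 3 = 5 neuropsychiatric triggers.

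| Trigger in Section 7.1 | Withdrawal on study | Stand-alone exclusion at the Screening Visit |
|---|---|---|
| Question 4 'Yes' (item 10) | Investigator judgment | Yes: criterion 12, second bullet |
| PHQ-9 15 to 19, up 3 points (item 10) | Investigator judgment | Yes: criterion 13 |
| Question 5 'Yes' (item 11) | Mandatory | Yes: criterion 12, second bullet |
| PHQ-9 of 20 or more (item 11) | Mandatory | Yes: criterion 13 |
| Any suicidal behavior (item 11) | Mandatory | No: only with an attempt within 5 years or Question 4/5 'Yes' |

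A 'Yes' to Question 4 or 5 meets both the stem and the second bullet, because Section 7.1 itself calls it active suicidal ideation. So 4 of the 5 triggers exclude on their own and 5 − 4 = 1 does not. For Question 4 and for PHQ-9 15 to 19, entry is stricter than the on-study rule. Suicidal behavior is the one trigger that runs the other way.

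This count holds at the Screening Visit. The PHQ-9 is repeated at Baseline, but criterion 13 names only the Screening score, so a score of 20 or more first seen at Baseline has no stand-alone exclusion either.

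**Step 3: is there behavior that is not an attempt?** SAP Section 5.6.3.9 defines suicidal behavior by 4 categories, whose names are not shown in the public text. SAP Table 7 lists preparatory acts apart from a suicide attempt. That table belongs to a separate adjudication scale. It shows that the two can be distinguished, not how the C-SSRS divides them.

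**The case against.** Several points on the other side have force.

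- **Entry rules need not mirror stopping rules.** New behavior on blinded treatment and history before the study are different questions. This stands. A reader might infer that Sections 5.2 and 7.1 contradict each other. They do not, because item 11 covers events since the last visit.
- **Section 7.1 may already catch the case.** Its closing paragraph asks for immediate referral for any suicidal ideation or behavior and states the withdrawal rule without a time limit, and Section 10.1.3 counts a participant as enrolled from consent. So it can be argued to catch behavior between Screening and Baseline. But Section 7.1 governs discontinuation of treatment. It is not an entry criterion, and item 11 does not reach back before Screening.
- **Criterion 15 is a backstop.** True. A reader might infer that the protocol lets suicidal participants in unnoticed. It does not: a 'Yes' to Question 4 or 5 in the past month excludes, as does a Screening PHQ-9 of 15 or more. Trained staff give the C-SSRS twice before dosing, so the profile would be seen. What is missing is an automatic rule.
- **The gap may be narrow.** 'Suicide attempt' is not defined and the four categories cannot be read. A wide reading of 'attempt' shrinks the gap. This stands, and it limits any claim about size.
- **Redundancy proves little.** One might argue that the behavior phrase adds no one whom the bullets miss. That is true of any rule of the form 'X and Y' compared with Y alone, such as the hepatitis C antibody plus confirmatory test in criterion 3. Counting logical combinations says nothing about participants and is not used here as a measure of size.

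**Conclusion.** The concern holds in limited form, as a minor point and a cheap improvement. On the printed wording, recent suicidal behavior that is not an attempt, with Questions 4 and 5 'No' and a Screening PHQ-9 below 15, is left to Investigator judgment, while new suicidal behavior on study forces withdrawal. At the Screening Visit this is 1 of 5 neuropsychiatric triggers without a stand-alone entry exclusion.

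That the gap exists follows from the printed 'and'. Its width rests on the assumption that the C-SSRS records at least one kind of suicidal behavior that sites would not call an attempt, which the public text cannot confirm. The documents give no rate from which to estimate how many of about 45 participants would be affected; few are to be expected. The consequence is a possible safety risk and uneven eligibility decisions between sites. The efficacy endpoints are not affected.

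**What to change.** Replace the joining words at the end of the stem of criterion 12 so that any one of the following excludes:

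1. active suicidal ideation on the C-SSRS, as the stem now has it, including a 'Yes' to Question 4 or 5 in the past month;
2. suicidal behavior on the Screening or Baseline C-SSRS within a stated look-back, by default the 5 years already used for attempts;
3. a suicide attempt within 5 years of Screening.

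Keep the mental health evaluation for attempts more than 5 years ago, and keep criterion 15. Item 1 must stay on the list; otherwise the rewording would drop active ideation alone, which two of the four readings exclude.

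The cost is one reworded criterion and an updated eligibility checklist. The C-SSRS is already given at both visits, so no assessment is added. The downside is possibly a very few more screen failures: from item 2, and from item 1 at sites that now read the stem as joined to the bullets.
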